Using the order in which participants complete Part 2 as an identifier, the participants from the mTBI-only and mTBI+PTSD groups will be randomly assigned to receive either treatment or delayed treatment, and then ranked in random order for participation in Part 2. Each of the groups will be populated using this selection procedure. The assignments will be determined at the onset of the study by the PI with subsequent replacement as needed. Because Part 2 is preliminary in nature (not a randomized control trial) and includes low numbers of participants, any participants opting out of Part 2 will be replaced using the rank ordered list. Participants will be informed at the conclusion of Part 1 whether they can enroll in Part 2. If participants do not qualify, they will be informed that they could be contacted at a later date to act as a replacement. The study staff will be responsible for discussing enrollment in Part 2 with participants.

Payment

The veteran participants will be paid \$50 per session (laboratory and home visits) for their participation, and a \$25 travel allowance for each session requiring travel to one of the testing sites. They will be paid through the preferred method at each site (e.g., Financial Management System, vouchers, payment cards). When the Financial Management System is used the payment will not be immediate. The significant others who complete the HHIA-SO will not receive any payment.

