Primary Analyses – Basic descriptive statistics will be computed and examination of statistical assumptions will be performed for all study measurements. For questionnaire data, analysis of variance (ANOVA) or Kruskal Wallis test will be used to determine differences in the overall and subset scores between the mTBI groups. The analysis will also include basic descriptive statistics for behavioral data test measures at baseline and at 6 months for the mTBI-only and mTBI+PTSD groups, and at baseline and 12 months for the delayed-treatment groups. We will focus on the changes in the behavioral test measures from baseline to 6 months (mTBI-only and mTBI+PTSD treatment groups) and from baseline to 12 months (delayed-treatment groups). Specifically, paired t-test or Wilcoxon signed rank test will be used to determine change at 6 or 12 months and this test will be applied to each behavioral test measure separately. False discovery rate will be used to adjust the p-values for multiple hypotheses testing. All statistical analyses will be two sided and the significance level will be 0.05.

Secondary Analyses – For longitudinal analysis, the data will be modeled using linear-mixed models for which the outcome is the behavioral test measure across time. The predictors will include time, group and interaction between group and time. Covariates will be added to the model as needed. In addition, variables with a high Gini score from Part 1 will be correlated with final hearing aid results as a preliminary investigation of whether hearing aid benefit can be associated by any of the variables obtained above. We will measure correlations using either Pearson's or Spearman's correlation coefficient. We will adjust the p-values for multiple testing by using a false discovery rate method whenever more than one variable is being tested. Single-subject design metric also will be used to investigate individual responses to the hearing aid treatment.

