Sample Size and Power – This analysis will include data from 100 participants (25 for each group). For any comparisons of the four groups based on ANOVA with a significance level of 0.01 to account for multiple comparisons and a power of 0.80, an effect size of 0.38 or greater will be detectable. For the paired analyses described above, there is sufficient power (0.80) to detect an effect size of 0.50 (baseline versus 6 months) or 0.50 (baseline versus 12 months), or greater assuming a two-sided significance level of 0.01 to account for multiple comparisons. For the longitudinal modeling, there will be sufficient sample size to support the proposed modeling that will allow approximately 10 observations to be estimated for each parameter. The number of covariates in each model will depend on the sample size to insure that there are approximately 10 observations available for each parameter estimated. For correlation

based analyses, the study is powered (0.80) to detect correlations of 0.26 or greater in absolute value for a total sample size of 100.

Once the data are formatted and cleaned by a staff member at the VA Pittsburgh site under the supervision of the statistician, the data will be analyzed by the statistician.

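### Part 2's primary behavioural test is uncontrolled before-after change: the delayed arm is scored at 12 months, so its randomly assigned untreated six months never serve as a comparison

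*Combined protocol and SAP*

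**What the plan says.** Section 5.2 (Part 2) says that participants from the two mTBI groups "will be randomly assigned to receive either treatment or delayed treatment". Section 5.1 (Delayed-Treatment Control Group) tests the delayed arm unaided at entry and visits it at 1, 2 and 4 months for questionnaires only. At month 6 it starts that arm on the treatment-group procedures.

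Section 5.6 (Part 2, Primary Analyses) examines change in each behavioural measure over baseline to 6 months in the treated groups "and from baseline to 12 months (delayed-treatment groups"). The test is a "paired t-test or Wilcoxon signed rank test will be used to determine change at 6 or 12 months", run separately for each measure.

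Three other elements come near a controlled comparison:

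- **ANOVA or Kruskal-Wallis (primary).** Its purpose is to "determine differences in the overall and subset scores between the mTBI groups", but it is assigned to questionnaire data and has no stated time point or baseline adjustment. The power section does refer more broadly: "For any comparisons of the four groups based on ANOVA".
- **Mixed model for behavioural measures (secondary).** "The predictors will include time, group and interaction between group and time". Neither the coding of time nor any specific contrast is given.
- **Same-session testing with and without aids** at 1 week and 6 months (section 5.1, Follow-up Testing and Home Visits). Section 5.6 does not mention this contrast, and the test order is not stated.

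**The concern.** A within-arm change from baseline adds together the effect of amplification, practice on the test, the passage of time and regression to the mean. A concurrent untreated arm is what separates them. This design creates one by random assignment, but the primary behavioural test looks at that arm only after it too has been treated.

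Practice is a concrete risk. The California Consonant Test (CCT) and the phonetic context task are not listed in Part 1 and first appear at the Part 2 baseline, so their first retest gain falls wholly inside the tested interval. Some practice on the Computerized Revised Token Test is already absorbed in Part 1.

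Specific question d in section 3.0 asks whether veterans both perceive and show benefit, and the study is meant to support a larger intervention study. A practice gain read as benefit would carry forward into that study.

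**Working it through.** **Inputs.** Section 5.6 gives 25 per group, four groups, power 0.80, two-sided 0.01 in the power statement, and 0.05 with false discovery rate adjustment in the analysis text. Drift, baseline correlation r and dropout are not in the documents and are assumed below. Power is from the noncentral F with 1 numerator df.

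**1. The plan's own figure.** The plan says: "For the paired analyses described above, there is sufficient power (0.80) to detect an effect size of 0.50 (baseline versus 6 months"), and the same for 12 months. For a paired test the noncentrality is λ = n·d², with n − 1 df.
- n = 50 (both PTSD strata pooled within an arm): λ = 50 × 0.25 = 12.5, power 0.799 at 0.01. The figure reproduces.
- n = 25 (a single group): power 0.402; the detectable effect is 0.735.

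The stated power is therefore that of an uncontrolled change in 50 people.

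**2. What drift alone does to the paired test.** Set the device effect to zero and put the drift in as d. The table gives the chance of a significant result per test, before false discovery rate adjustment.

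| Assumed drift (SD of change) | n=50, 0.05 | n=50, 0.01 | n=25, 0.05 | n=25, 0.01 |
|---|---|---|---|---|
| 0.2 | 28% | 11% | 16% | 5% |
| 0.3 | 55% | 30% | 30% | 12% |
| 0.5 | 93% | 80% | 67% | 40% |

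**3. CCT and phonetic context administrations before the endpoint session.**
- Treated, month 6: pre-fitting, 1 week aided, 1 week unaided = 3.
- Delayed, month 12: entry, month-6 pre-fitting (implied), 1 week aided, 1 week unaided = 4.
- Delayed, month 6: entry = 1.

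**4. The controlled month-6 contrast, 50 v 50.**
- Unadjusted change: λ = (n/2)·d² = 25 × 0.25 = 6.25 at d = 0.50, with 98 df. Power is 0.453 at 0.01 and 0.697 at 0.05. The detectable effect at 0.01 is 0.70, and 0.80 power at 0.50 needs 96 per arm.
- ANCOVA with baseline and stratum: residual SD ÷ SD of change = √(1−r²) ÷ √(2(1−r)) = √((1+r)/2), so λ = 25·d² ÷ ((1+r)/2), with 96 df.

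| r (assumed) | Detectable, 0.01 | Power at 0.50, 0.01 | Power at 0.50, 0.05 | n per arm for 0.80, 0.01 |
|---|---|---|---|---|
| 0.3 | 0.56 | 0.68 | 0.87 | 63 |
| 0.5 | 0.60 | 0.60 | 0.82 | 72 |
| 0.7 | 0.64 | 0.54 | 0.77 | 82 |

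Effects are in SD of change, the plan's paired unit. In raw-score SD, 0.50 equals 0.50 × √(2(1−r)) = 0.59, 0.50 or 0.39, so the rows are not the same raw effect. For a fixed 0.50 raw SD, power at 0.01 rises with r: 0.50, 0.60, 0.81.

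**5. What the controlled contrast leaves.** Take total drift of 0.2, 0.3 or 0.5 with r = 0.5. If half of it is specific to the treated arm, the ANCOVA rejects at 0.05 in 9%, 14% or 30% of trials. If three-quarters is, the rates are 14%, 25% or 57%. If all of it is, they are 21%, 40% or 82%.

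**6. Replacement.** Section 5.2 says "any participants opting out of Part 2 will be replaced using the rank ordered list". Suppose there is no device effect, only the treated arm loses and replaces people, and leaving has correlation ρ with a poor adjusted month-6 score. The bias is ρ·√0.75·φ(z_q)/(1−q), where q is the proportion leaving.
- ρ = 0.3, q = 10%, 20% or 30%: 0.05, 0.09 or 0.13 SD; simulated rejection at 0.05 is 6%, 8% or 12%.
- ρ = 0.5: 0.08, 0.15 or 0.21–0.22 SD; rejection 7%, 14% or 24%.
- Equal loss in both arms gives bias near zero and rejection of 4–6%.

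**The case against.** The strongest reply is that the controlled information is collected and partly analysed. The mixed model would use the untreated months if the delayed arm takes the battery before fitting at month 6. Same-session aided and unaided scores hold calendar time and most practice constant. Part 2 is also secondary, preliminary, and by the plan's own account not a randomised controlled trial.

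Much of this is fair, and it lowers the severity. It does not remove the point. The mixed model ranks second and names no month-6 contrast, and the same-session contrast is not in the analysis section. That contrast would also miss benefit carried into unaided listening, which the Treatment Options section anticipates through lasting change in central auditory processing. Preliminary status limits how firm conclusions can be; it does not enable a paired test to separate practice from amplification.

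Three further objections stand as limits. The drift sizes are assumed, and the 0.05 rates before adjustment are upper bounds. The month-6 contrast does not equalise practice (3 prior administrations v 1). The replacement bias in step 6 depends on loss being concentrated in the treated arm, and it concerns the remedy, not the present plan.

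**Conclusion.** The concern holds and should be fixed. No primary behavioural test in Part 2 uses the randomly assigned untreated period as a comparison, and the stated detectable effect of 0.50 belongs to an uncontrolled change in 50 people. With no device effect, assumed drift of 0.2 to 0.5 SD of change would make the paired test significant in 28% to 93% of trials at 0.05 unadjusted, or 11% to 80% at 0.01 (n = 50). These rates illustrate the risk; they do not estimate the actual practice effect.

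The 50 v 50 figures assume a delayed group in each PTSD stratum, as section 5.2 (Part 2) and the four groups of 25 in section 5.6 imply. Section 5.1 instead draws the delayed group from mTBI-only, and these passages must be reconciled. With mTBI-only delayed participants alone, a like-for-like 25 v 25 comparison of change detects only about 1.00 SD at 0.01. The flaw in the paired test exists on either reading.

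**What to change.** 1. Make the primary Part 2 test of benefit the month-6 comparison of treatment with delayed treatment: ANCOVA on the month-6 score with Part 2 baseline and PTSD stratum, or the same contrast from the mixed model with categorical time.
2. Name the treated arm's aided month-6 score as the outcome. Report the same-session aided v unaided contrast as supporting, with test order stated or counterbalanced.
3. State in section 5.1 that the delayed arm completes the unaided questionnaires and the speech and language battery at month 6 before fitting. The text implies this but names only pure-tone thresholds. Reconcile sections 5.1 and 5.2 on which strata supply the delayed arm.
4. Analyse everyone who starts Part 2 in the arm assigned, include available month-6 data from those who stop, and report declines and replacements by arm, before and after the Part 2 baseline.
5. Keep the paired changes as supporting, including the delayed arm's month 6 to 12 change. Treat the treatment-by-PTSD interaction as exploratory: with 25 per cell it has 80% power only for about 1.2 SD at 0.01 (r = 0.5).
6. Restate the Part 2 power for the new contrast, and state the remaining limits: unequal practice at month 6, and expectancy because delayed veterans know they are unaided.

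**Cost.** The changes are to the text of sections 5.1, 5.2 and 5.6. No new participants are needed, and no new visits if the month-6 battery is given as implied; collecting month-6 data from those who stop takes extra effort. The real cost is power at 0.50 and 0.01, which falls from 0.80 to 0.45 unadjusted, or to 0.54–0.68 with ANCOVA. The plan should accept and state the larger detectable effect.

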Follow-up Testing – The participants will be followed over a 6-month period. One week (+/- 3 days) after the fitting the participants will be seen in the lab to re-verify the fit of their hearing aids and to determine any problems. The hearing aid use-time will be recorded from the data-logging system of the hearing aids as a reflection of hearing aid benefit and to document the extent to which the participants are wearing their hearing aids. During this session, both the aided and unaided portions of the APHAB will be administered along with the International Outcomes Inventory for Hearing Aids (IOI-HA; Cox & Alexander, 2002). In addition, the participants will answer a single question about their likelihood to continue hearing aid use. Intent to continue use tends to be related to user satisfaction with commercial products and service provision in other areas of healthcare. The participants also will complete the HHIA, and SSQ. The CCT, CRTT, CRTT-R and the phonetic context effect tasks will be re-administered with and without hearing aids.

Home Visits – The participants will be visited in their homes by study staff at three different times: 1-, 2- and 4-months post-fitting (+/- 1 week). The home visits will occur to reduce participant burden and encourage retention. However, some participants might prefer to be seen in the lab or clinic than their homes, and if that is the case those participants will be accommodated. Hearing aid use-time will be recorded from the data-logging system of the hearing aids and the hearing aids will be checked to determine appropriate function. During these visits the HHIA, SSQ, APHAB, IOI-HA, and the intent to continue use question will be re-administered. New hearing aid batteries will be provided and participants will be encouraged to wear their hearing aids for longer periods of time if their use-time is below 8 hours a day. At 6-months post-fitting (+/- 1 week) the laboratory follow-up testing will be repeated.

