Delayed-Treatment Control Group – The participants in the delayed-treatment control group will be selected from the mTBI-only group and followed over a 12-month period (+/- 2 weeks). At the onset of Part 2 they will complete the HHIA, SSQ, and the unaided portion of the APHAB. They will complete the speech perception and language tasks administered to the treatment group (CCT, phonetic context effect, and CRTT tasks) but unaided only. The delayed-treatment groups will receive home visits at 1, 2, 4 months (+/- 1 week) post-entry, at which times they will complete the HHIA, SSQ, and the unaided portion of the APHAB. At 6 months post-entry their pure tone hearing thresholds will be measured to determine possible changes in hearing sensitivity, and the procedures used with the treatment groups will be applied with the same sequence of follow-up sessions.

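### The Part 2 mixed model has no term for whether aids are fitted, so depending on a time coding the plan does not state, it can miss a real hearing aid effect

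*Combined protocol and SAP*

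**What the plan says.** Section 5.6 (Part 2, Secondary Analyses) plans "linear-mixed models for which the outcome is the behavioral test measure across time". It continues: "The predictors will include time, group and interaction between group and time", and then "Covariates will be added to the model as needed". It does not say whether time is continuous or categorical, whether it runs from entry or from fitting, which visits enter, or which contrast measures benefit.

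Section 5.1 sets the schedule. For the treatment groups, "The participants will be followed over a 6-month period". The first test after fitting is early: "One week (+/- 3 days) after the fitting the participants will be seen in the lab". At that session "The CCT, CRTT, CRTT-R and the phonetic context effect tasks will be re-administered with and without hearing aids". The last is "At 6-months post-fitting (+/- 1 week) the laboratory follow-up testing will be repeated". The home visits at 1, 2 and 4 months list questionnaires and no behavioral tests.

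The delayed groups are tested unaided at entry and followed for 12 months. At month 6 their pure-tone thresholds are measured and "the procedures used with the treatment groups will be applied with the same sequence of follow-up sessions".

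Section 5.2 (Part 2) defines four groups of 25, mTBI-only and mTBI+PTSD crossed with immediate and delayed fitting. Assignment is random, and participants who opt out are replaced from a ranked list. The same section calls Part 2 preliminary and says it is not a randomized controlled trial.

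**The concern.** The delayed arms exist so that change with aids can be set against change without them. In this design that comparison is available only from entry to month 6. Afterwards both arms have been fitted, and a model that knows only group and time cannot tell the delayed arms' unfitted months from their fitted ones.

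The primary behavioral analysis is a set of within-group paired tests, and the ANOVA is assigned to questionnaire scores. The mixed model is therefore the only planned analysis that compares behavioral change between immediate and delayed arms. If its interaction is read as the test of benefit, some natural ways of fitting it would return a null result when the aids work. Section 3.0 says the study is meant to support a larger intervention study, and a false null could misdirect that study.

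**Working it through.** **Inputs from the documents.** Behavioral test times in months from entry are 0, 0.25 and 6 for the immediate arms (5.1). For the delayed arms they are taken as 0, 6 (before fitting), 6.25 and 12; the month-6 pre-fitting test is implied by 5.1 but not listed. There are four groups of 25, so 50 immediate and 50 delayed (5.2, 5.6). The test is two-sided at alpha 0.05 (5.6).

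**Assumptions not in the documents.** The effect d is 0.5 SD of a single score and equal in all arms. There is no practice trend. Errors follow a random-intercept model with within-person correlation ρ of 0.3 to 0.7.

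**The plan's own figure.** No power is given for the interaction. The nearest figure is the paired effect size of 0.50 at 80% power and two-sided alpha 0.01. The noncentral t gives power 0.799 with n = 50 and 0.40 with n = 25, so the figure reproduces if two groups are pooled. It is in units of the SD of change, which equals the score SD when ρ = 0.5. I use 0.5 for scale.

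**Step 1: linear months from entry, full step at fitting.** Everyone in an arm shares the same test times, so the expected slope is b = Σ(t − t̄)y / Σ(t − t̄)².

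- Immediate: t̄ = 2.0833, y = (0, d, d). b = (−1.8333 + 3.9167)d / 23.042 = 0.0904d per month.
- Delayed: t̄ = 6.0625, y = (0, 0, d, d). b = (0.1875 + 5.9375)d / 72.047 = 0.0850d per month.
- Difference: 0.0054d per month. Over 6 months at d = 0.5 this is 0.0054 × 6 × 0.5 = 0.016 SD, about 3% of the true effect.

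The 3-df group-by-time test has power of about 0.05 at ρ = 0.3, 0.5 and 0.7, which is no more than alpha.

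**Step 2: other codings with the same step.**

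- Baseline versus final visit as two levels: both arms change by d, so the interaction is exactly 0.
- Time since fitting, using the pre-fit, 1-week and 6-month tests in each arm: both slopes are 0.0904d, so the interaction is exactly 0. Keeping the delayed arms' entry test at −6 months returns 0.0054d, because moving the origin does not change a slope.
- Linear months, first and last visit only: d/6 − d/12 = 0.083d per month. This reflects visit spacing, not benefit.
- Linear months cut off at month 6: 0.0904d against 0. Power is 0.23 to 0.46 with 50 per arm.

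**Step 3: benefit that builds linearly over 6 months.** The immediate slope is d/6 = 0.1667d. For the delayed arms y = (0, 0, 0.0417d, d), so b = (0.1875 × 0.0417 + 5.9375)d / 72.047 = 0.0825d. The difference over 6 months at d = 0.5 is 0.25 SD, half the effect. The 3-df test has power 0.21 to 0.45.

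**Step 4: visits as categories from entry.** Four groups by five occasions give 20 cells. Six are empty: two delayed groups at 0.25, and two immediate groups at each of 6.25 and 12. The 14 filled cells less 8 main-effect parameters (1 + 3 + 4) leave 6 interaction df. All four groups share months 0 and 6, so the month-6 contrast is estimable and equals d − 0 = 0.5 SD. Its standard error is √[2(1 − ρ)(1/50 + 1/50)], and the overall 6-df test has noncentrality z².

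| ρ | SE | z | Power, month-6 contrast | z² | Power, 6-df test |
|---|---|---|---|---|---|
| 0.3 | 0.237 | 2.11 | 0.56 | 4.46 | 0.30 |
| 0.5 | 0.200 | 2.50 | 0.71 | 6.25 | 0.42 |
| 0.7 | 0.155 | 3.23 | 0.90 | 10.42 | 0.67 |

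**The case against.** A reader might infer that the interaction is near zero whatever is done, so that the plan as written must report no difference. The documents do not support that. They leave time coding and visit window open, and with visit categories from entry the stated terms already contain the full effect at month 6. The near-zero figure also needs a benefit complete within a week. Section 2.0 (Treatment Options) expects little change in signal-to-noise ratio and suggests perceptual learning and central reorganization, which fits gradual build-up better; there the interaction is about half the effect.

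The sponsor can add that section 5.6 never names the interaction as the test of benefit, and that group also encodes PTSD status. A PTSD comparison between arms on the same schedule is a legitimate use of group-by-time. The model is secondary, the primary paired tests are unaffected, and Part 2 is called preliminary.

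All of this stands, and it limits the severity. It does not remove the point. The plan names neither the coding nor the contrast that would work, so the same data could yield none, half or all of the effect. The open provision for covariates neither supplies nor excludes a fitted term, and would leave that choice until after the data are seen.

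A fitted indicator alone is not a complete remedy either. It does not separate aided from unaided scores, both of which are collected after fitting, and the month-6 contrast needs a delayed-arm test that is only implied.

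**Conclusion.** The point holds in conditional form. The stated model has no fitted term although the delayed arms enter treatment at month 6, and several natural time codings would hide a real effect. For a 0.5 SD step, the immediate-versus-delayed interaction is 0.016 SD per 6 months with linear months. It is exactly zero with baseline-versus-final coding, or with time since fitting on matched visits. It is about 0.25 SD if benefit builds linearly. With visit categories the month-6 component is the full 0.5 SD, diluted in the 6-df test.

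These sizes rest on the assumed effect, equal benefit in all arms, no practice trend, ρ of 0.3 to 0.7 and a month-6 pre-fitting test in the delayed arms. They also follow sections 5.2 and 5.6 in having two delayed groups, although 5.1 draws the delayed group from mTBI-only.

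This should be fixed but is not critical, because it concerns a secondary analysis in a preliminary part. A reader might also treat the month-6 comparison as a fully randomized one; the replacement of opt-outs in section 5.2 means it should not be described so without qualification.

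**What to change.** Amend the Part 2 secondary analysis in section 5.6 as follows.

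1. Code time as visit categories in months since entry.
2. Include PTSD stratum, a time-varying fitted indicator (0 before fitting, 1 after; 0 for the delayed arms through the month-6 pre-fitting test) and fitted-by-PTSD.
3. Prespecify the month-6 contrast, immediate arms fitted against delayed arms not yet fitted, as the between-arm estimate of the hearing aid effect. Treat delayed-arm change from month 6 to 12 as supporting within-person evidence.
4. State whether aided or unaided post-fitting scores enter, and model the two separately.
5. Confirm in section 5.1 that the delayed arms take the behavioral battery at month 6 before fitting. The contrast depends on it.
6. Describe the contrast as based on random assignment with replacement of opt-outs.

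If the month-6 battery is confirmed, this needs wording only, with no new visits. The cost is a few more parameters and a benefit estimate that rests mainly on the first 6 months.

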- b. Are certain test procedures and stimuli particularly sensitive to the deficits found with this population of veterans and are deficit patterns influenced by the coexistence of PTSD?
- c. Does the addition of background noise produce over-additive effects in this population of veterans and does PTSD increase the effect?
- d. Does this population of veterans perceive and demonstrate benefit when fitted with hearing aids that provide mild high-frequency gain and does PTSD influence benefit?
- e. Is hearing aid benefit predictable by measures of auditory processing, speech perception, psychoacoustic, verbal working memory, and language processing? Furthermore, does the coexistence of PTSD influence the relationship between these measures and hearing aid benefit?

Expected Outcomes

- a. This population of veterans will differ from veterans with no history of blast exposure, and the presence of PTSD will increase severity and alter the deficit pattern.
- b. This population of veterans will experience significant problems with the addition of background noise and the effect will be influenced by linguistic load, verbal working memory and attention.
- c. This population of veterans will demonstrate and perceive benefit from being fitted with mild-gain high-frequency hearing aids, although the coexistence of PTSD will restrict perceived benefit.
- d. Mild-gain high-frequency amplification will improve speech perception skills in quiet and noise, and improve linguistic processing and executive function.
- e. Benefit from amplification will relate to the deficits that the veterans present.

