5.6 Data Analysis

Part 1 Analysis

Preliminary Analyses - The analysis will begin with basic descriptive statistics including means and standard deviations for continuous data and examination of distributional assumptions for all study measurements including the questionnaire data (e.g., HHIA, WHODAS-II, SSQ and HHIA-SO) for each group of interest. These analyses will be used to evaluate the extent of missing data and to identify outliers.

Primary Analyses - Random Forests (RF, Breiman, 2001) will be applied to determine which auditory, language processing, and executive function variables best discriminate the three groups. This technique performs variable selection and the variables are ranked by Gini score, a measurement of average accuracy of all trees containing a particular variable. One-way ANOVA will be used to determine differences between groups for normally distributed continuous data. Analysis of covariance (ANCOVA) will be used to adjust for differences between groups. If assumptions for the parametric test are not met, a non-parametric alternative will be used (e.g., Kruskal-Wallis, non-parametric ANCOVA). The p-values will be adjusted for multiple testing by using a false discovery rate method whenever more than one variable is being tested. Statistical assumptions (e.g., linearity, normality) will be verified prior to hypothesis testing. All statistical analyses will be two sided and the significance level will be 0.05.

Sample Size and Power - A sample size of 117 per veteran group will achieve 80% power at a 0.05 significant level to detect an effect size (i.e., odds ratio) of 2.50. This sample size was computed based on an adjustment that was made assuming that a multiple regression of the independent variable of interest on the other independent

variables in the model will result in an R-squared of 0.20. For one-way ANOVA, the total sample of 468 subjects achieves 80% power to detect an effect size of 0.18 or larger with a two-sided significance of 0.01 to account for multiple hypotheses testing. For analysis of covariance, the study is powered (0.80) to detect an effect size of 0.16 assuming the strength of the relationship between the response of interest and the covariates, measured as R-squared, is 0.20.

Part 2 Analysis

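### The PTSD half of question e has no planned analysis, and the hearing aid outcome to be correlated with the Part 1 measures is neither defined nor baseline-adjusted

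*Combined protocol and SAP*

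**What the plan says.** Section 3.0, question e, has two parts. The first asks whether hearing aid benefit is predictable from the Part 1 measures. The second asks: "does the coexistence of PTSD influence the relationship between these measures and hearing aid benefit".

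Section 5.6 (Part 2, Secondary Analyses) answers with one analysis: "variables with a high Gini score from Part 1 will be correlated with final hearing aid results", described "as a preliminary investigation of whether hearing aid benefit can be associated by any of the variables obtained above". The statistic is bivariate: "We will measure correlations using either Pearson's or Spearman's correlation coefficient". P-values are adjusted by false discovery rate. No instrument, visit or handling of the pre-fitting score is given for these correlations. Change from baseline is specified only for the paired tests in the Primary Analyses.

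The same paragraph plans a linear mixed model of the behavioral measures: "The predictors will include time, group and interaction between group and time". Covariates may be added as needed.

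The Part 2 sample size paragraph gives 80% power for an absolute correlation of at least 0.26 with all 100 participants. Section 5.2 makes these four groups of 25, two mTBI-only and two mTBI+PTSD.

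**The concern.** The first problem is a research question without an analysis. A pooled correlation gives one number for both PTSD strata together. It cannot show whether the relation differs between them.

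The second is an outcome that may not be benefit. Section 5.1 collects two kinds of post-fitting data. Use-time (which the protocol treats as reflecting benefit), IOI-HA and the aided and unaided APHAB express benefit or can be scored to do so. CCT, CRTT, CRTT-R, HHIA and SSQ have pre-fitting values, and their final score alone is a level that carries the participant's starting point. CRTT and CRTT-R are the clearest case: they belong to the Part 1 battery and are also Part 2 outcomes, so correlating them with their own final score would largely show test-retest stability.

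At stake is whether Part 2 could report predictors of benefit that are partly markers of severity, and whether it would have anything to say about PTSD as a modifier of prediction.

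**Working it through.** **The plan's own figure.** Inputs from section 5.6: N = 100, power 0.80, two-sided 0.05 (the general Part 2 level; none is attached to the correlation line). By Fisher z, the detectable r = tanh((1.960 + 0.842)/√97) = tanh(0.2845) = 0.277. The stated 0.26 is not reproduced: one-sided 0.05 gives 0.247 and two-sided 0.01 gives 0.334. Power at r = 0.26, two-sided 0.05, is 74.6%. This is a side observation. What matters here is that the line treats 100 people as one sample.

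**Is PTSD moderation tested anywhere?** The correlations contain no PTSD term. The mixed model's group-by-time term asks whether groups change differently, which is question d. Moderation of prediction would need a Part 1 measure crossed with PTSD and time. Adding a covariate as needed does not supply that.

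**What a moderation test could detect.** Compare two independent correlations: Δz = (1.960 + 0.842) × √(2/(n − 3)).
- n = 50 per stratum: 2.802 × √(2/47) = 0.578, for example r = 0 versus 0.52.
- n = 25 per stratum (immediate-treatment groups only): 2.802 × √(2/22) = 0.845, for example r = 0 versus 0.69.
- Power for r = 0 versus 0.26 with n = 50: atanh(0.26) = 0.266; 0.266/0.206 − 1.960 = −0.67, giving 25%. Reaching 80% needs 2 × (2.802/0.266)² + 3, about 225 per stratum.

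The 50 v 50 split follows section 5.2 and the total of 100 in section 5.6. The delayed-treatment paragraph of section 5.1 mentions selection from the mTBI-only group alone.

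**Final score versus change.** Let final F = baseline B + change C. Suppose Part 1 measure X correlates a with B and 0 with C, B and C are uncorrelated, and q = SD(C)/SD(B). Then corr(X, F) = a/√(1 + q²). The documents give neither a nor q, so both are assumed over a range. Brackets show the chance of unadjusted p < 0.05 at N = 100.

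| a | q = 0.5 | q = 1.0 |
|---|---|---|
| 0.3 | 0.27 (77%) | 0.21 (56%) |
| 0.5 | 0.45 (99.7%) | 0.35 (95%) |
| 0.7 | 0.63 (about 100%) | 0.49 (about 100%) |

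X has no relation to change in any cell. A different model gives similar values. If benefit is constant and X correlates 0.6 (assumed) with true severity, corr(X, F) = 0.6 × √retest, which is 0.42, 0.50 and 0.54 for retest correlations of 0.5, 0.7 and 0.8.

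The error can also hide a real predictor. If X correlates 0.4 with change and −0.2 with baseline, and q = 0.5, the numerator is −0.2 + 0.4 × 0.5 = 0, so corr(X, F) = 0.

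**Pooling across PTSD groups.** With no within-group correlation and an assumed gap of g SD between equal groups on both variables, pooled r = (g²/4)/(1 + g²/4): 0.06 at g = 0.5, 0.14 at g = 0.8 and 0.20 at g = 1.0.

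**The case against.** The planned sentence names benefit as its target, and several post-fitting measures do express benefit. If the final results mean use-time, IOI-HA or an APHAB benefit score, the baseline artefact is not shown. This stands, and it makes the second half of the point conditional on which outcome is used.

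The sizes rest on assumed correlations. This also stands: the 0.21 to 0.63 range illustrates the problem and does not estimate it. The pooling artefact is modest. At r = 0.14 to 0.20 it lies below the plan's own 0.26 and would reach unadjusted p < 0.05 only about 28% to 51% of the time. The false discovery rate adjustment is no answer to the baseline problem, because it limits chance findings and does not correct a mis-specified outcome.

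A reader might also infer that Gini screening is the wrong filter, since it ranks variables that "best discriminate the three groups" and not those that vary with benefit. The documents do not support calling this an error. Expected outcome e in section 3.0 is that benefit relates to the veterans' deficits, so screening on deficit measures fits that hypothesis and keeps the family of tests small.

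Finally, the analysis is secondary, Part 2 is described as preliminary, and a moderation test would be imprecise. That argues for an exploratory label. It does not explain why a listed question has no analysis.

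**Conclusion.** The PTSD half of question e has no stated analysis, and the plan followed exactly cannot answer it. This conclusion needs no assumption beyond the text.

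The benefit half holds conditionally. The outcome, its visit and the handling of the pre-fitting score are not specified. If raw final CCT, CRTT, CRTT-R, HHIA or SSQ scores are used, the correlation mixes starting severity with benefit: about 0.21 to 0.63 for a measure unrelated to change, given a = 0.3 to 0.7 and q = 0.5 to 1.0.

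A reader might infer that the analysis measures only who scores well and that any predictor found would be a mere marker of severity. The text does not establish that, because the outcome is left open and some candidates express benefit.

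This should be corrected before analysis. It affects a secondary, preliminary analysis, not the Part 1 comparisons.

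**What to change.** In section 5.6, name the outcomes and the visit: 6 months after fitting, which is the 12-month visit for the delayed-treatment groups. Then:

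- For each outcome with a pre-fitting score, replace the raw correlation with a regression of the final aided score on its pre-fitting score, the Part 1 measure, PTSD group and measure-by-PTSD. State which pre-fitting score applies to the delayed groups. Adjusting for the pre-fitting score is preferable to aided minus unaided at the final visit. Section 2.0 suggests that benefit may come through central reorganization, and that difference would subtract any gain also present unaided.
- For use-time and IOI-HA, which have no pre-fitting value, fit the same model without that term.
- Keep the false discovery rate adjustment. Report the interaction as exploratory, as an estimate with a confidence interval.

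The cost is SAP wording and modest analysis time; no new data are needed. The downside is imprecision: with 50 v 50 only a Fisher-z difference of about 0.58 is detectable with 80% power, and a non-significant interaction must not be read as showing that PTSD has no influence.
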